### 3.1.2 Study Treatment Phase

Following informed consent (assent when applicable) and prior to enrollment into any of the study phases (Phases I, IIA and IIB), female patients  $\geq$  10 years of age or those who have experienced the onset of menses must have a documented NEGATIVE pregnancy test (urine or blood).

In Phase I, all enrolled subjects will receive the TubeClear® intervention. Prior to the intervention, the location of the EAD(P) will be determined based on review of radiographs. The Investigator may obtain a new radiograph if the EAD(P) location is uncertain. The Investigator will determine the length and diameter of the EAD(P) from the EHR and/or the length marking (in cm) at the exit point of the EAD(P) from the body surface orifice. The Operator-set Collar on the clearing stem of TubeClear® will be placed corresponding to the EAD(P) measured length recorded by the Investigator. The TubeClear® Instructions for Use (i.e., Operator's Manual) will be followed by the user to restore patency to the EAD(P). EAD(P) patency restoration will be measured by the ability to flush the EAD(P) with 10 ml of air within five (5) minutes after completion of the intervention. After successful air flushing, aspirate will be extracted through the EAD(P), and the pH of the contents checked to confirm location according to CHOP standard of care. Following confirmation of correct EAD(P) placement, 5-20 ml of water will be flushed through the EAD to assure continued patency. Following the TubeClear® intervention, the Subject will receive an abdominal radiograph with contrast. A radiologist (blinded to the study) will assess the radiographs for adverse events (i.e., EAD(P) displacement, EAD(P) damage, enteral tract tissue injury) attributable to the intervention. If the TubeClear® intervention is unable to restore EAD(P) patency, further steps to restore patency of the occluded EAD will be determined by the clinical team per usual practice.

In Phase IIA, all enrolled subjects will receive the TubeClear® intervention. Prior to the intervention, the location of the EAD(P) will be determined based on review of radiographs. The Investigator may obtain a new radiograph if the EAD(P) location is uncertain. The Investigator will determine the length and diameter of the EAD(P) from the EHR and/or the length marking (in cm) at the exit point of the EAD(P) from the body surface orifice. The Operator-set Collar on the clearing stem of TubeClear® will be placed corresponding to the EAD(P) measured length recorded by the Investigator. The TubeClear® Instructions for Use (i.e., Operator's Manual) will be followed by the user to restore patency to the EAD(P). EAD(P) patency restoration will be measured by the ability to flush the EAD(P) with 10 ml of air within five (5) minutes after completion of the intervention. After successful air flushing, aspirate will be extracted through the EAD(P), and the pH of the contents checked to confirm location according to CHOP standard of care. Following confirmation of correct EAD(P) placement, 5-20 ml of water will be flushed through the EAD to assure continued patency. Following the TubeClear® intervention, the Subject will receive an abdominal radiograph with contrast. A radiologist (blinded to the study) will assess the radiographs for adverse events (i.e., EAD(P) displacement, EAD(P) damage, enteral tract tissue injury) attributable to the intervention. If the TubeClear® intervention is unable to restore EAD(P) patency, further steps to restore patency of the occluded EAD will be determined by the clinical team per usual practice.

In Phase IIB, subjects will be randomized into either TubeClear® intervention or CHOP Standard Treatment using a predetermined computer generated randomization sequence stored in opaque sealed envelopes. Prior to the intervention, the location of the EAD(P) will be determined based on review of radiographs. The Investigator may obtain a new radiograph if the EAD(P) location is uncertain. The Investigator will determine the length and diameter of the EAD(P) from the EHR and/or the length marking (in cm) at the exit point of the EAD(P) from the body surface orifice. If randomized to TubeClear®, the Operator-set Collar on the clearing stem of TubeClear® will be placed corresponding to the EAD(P) measured length recorded by the Investigator. The TubeClear® Instructions for Use (i.e., Operator's Manual) will be followed by the user to restore patency to the EAD(P). If randomized to CHOP Standard Treatment, the CHOP protocol to restore patency to occluded EAD(P) will be followed. EAD(P) patency restoration will be measured by the ability to flush the EAD(P) with 10 ml of air within five (5) minutes after completion of the intervention. After successful air flushing, aspirate will be extracted through the EAD(P), and the pH of the contents checked to confirm location according to CHOP standard of care. Following confirmation of correct EAD(P) placement, 5-20 ml of water will be flushed through the EAD to assure continued patency. Following either intervention, the Subject will receive an abdominal radiograph with contrast. A radiologist (blinded to the study) will assess the radiographs for adverse events (i.e., EAD(P) displacement, EAD(P) damage, enteral tract tissue injury) attributable to the intervention. If either intervention is unable to restore EAD(P) patency, further steps to restore patency of the occluded EAD will be determined by the clinical team per usual practice.

### **3.1.3 Follow-up Phase**

Surveillance will include assessment for any adverse event(s) related to the intervention (i.e. EAD(P) displacement, EAD(P) damage, enteral tract tissue injury) and will continue for up to three (3) days following interventions in all study phases regardless of study intervention allocation. Clinical Assessment Measurements (i.e., pain, feeding tolerance, and usual measures to determine EAD(P) location) will be performed prior to, immediately following, and for up to three days after the intervention. Patients who are discharged from the hospital prior to three days will be followed up daily by phone for Clinical Assessment Measurements i.e., pain, feeding tolerance and EAD(P) location as assessed by caregiver until post Intervention day three.

## **3.2 Allocation to Treatment Groups and Blinding**

All Subjects in Phase I and Phase IIA of the Study will receive TubeClear® to restore patency of the occluded EAD(P).

All Subjects in Phase IIB will be randomized into the TubeClear® intervention (experimental) or CHOP Standard Treatment (control) group according to a predetermined computer generated randomization sequence. The randomization sequence will be kept in individual opaque sealed envelopes to be opened after the Subject is consented and enrolled in Phase IIB. To ensure an appropriate balance of participation in both the experimental and control groups, balanced, permuted block randomization will be used, as Phase IIB is not blinded.

### **3.3 Study Duration, Enrollment and Number of Sites**

#### **3.3.1 Duration of Study Participation**

The duration of study participation per Subject will be up to three (3) days in each phase following initiation of intervention. Clinical Assessment Measurements (i.e., pain, feeding tolerance, and usual measures to determine EAD(P) location) will be performed prior to, immediately following, and for up to three (3) days. Surveillance will include assessment for any adverse event(s) related to the intervention (i.e. EAD(P) displacement, EAD(P) damage, enteral tract tissue injury) and will continue for up to three (3) days. Patients who are discharged from the hospital prior to three days will be followed up daily by phone for Clinical Assessment Measurements i.e., pain, feeding tolerance and EAD(P) location as assessed by caregiver until post Intervention day three. The Subject's actual time spent receiving the study intervention will vary based on whether the Subject is randomized to the TubeClear® intervention or CHOP Standard Treatment. It is estimated that the TubeClear® intervention will take thirty (30) minutes per Subject, including time to prepare and set up the device. It is estimated that CHOP Standard Treatment will take four (4) hours per Subject, including time to prepare for the application of CHOP Standard Treatment.

#### **3.3.2 Total Number of Study Sites/Total Number of Subjects Projected**

The Study will be conducted at one site, the Children's Hospital of Philadelphia (CHOP) in the Pediatric Intensive Care Unit (PICU), Progressive Care Unit (PCU), and Interventional Radiology Department (IR). A total of 64 Subjects will be enrolled in this Study – 15 in Phase I and 49 in Phase II.

### **3.4 Study Population**

#### **3.4.1 Inclusion Criteria**

1. Males or females who have not attained their 18th birthday (Phase I)

Or

Males or females who have not attained their 11th birthday (Phase IIA)

Or

Males or females between 11 years of age and have not attained their 18th birthday (Phase IIB)

2. Indwelling occluded EAD(P) that is either:

- a. ND, NG, NJ tube composed of Polyvinyl Chloride (PVC) and Polyurethane 6 – 8 Fr, 38 – 140 cm; or
- b. NG tube (Corflo, Corpak MedSystems) used as a J tube inserted through a G tube, 6 – 8 Fr, 38 – 140 cm
- c. GJ tube (AMT) 14 Fr, 38 – 140 cm (15 – 55 in)

### **3.4.2 Exclusion Criteria**

1. Ward of the state
2. Positive pregnancy test/ Pregnant females
3. Any active gastrointestinal abnormalities or malformations, including but not limited to infections, inflammation, obstruction and/or recent abdominal surgery or trauma
4. Constant dependency on the EAD(P) for a glucose source (e.g. hyperinsulinism states)
5. Unable to tolerate water volume needed for the EAD(P) flush
6. Allergies to the contrast agent(s) used in post-Intervention radiological imaging
7. Measured total length of EAD(P) less than 38 cm (15 in) - from external port to EAD(P) distal end
8. Unknown length of EAD(P)
9. Attending physician declines enrollment based on clinical judgement
10. Subject attains 18 years of age during study duration

Subjects that do not meet all of the enrollment criteria will not be enrolled. Any violations of these criteria will be reported in accordance with IRB Policies and Procedures.

## 4 STUDY PROCEDURES

**Table 1** lists the study procedures in all study phases.

### 4.1 Screening Visit

- Potential eligible Subjects are patients in the PICU, PCU, or IR that are identified to have an occlusion of their EAD(P)s during the current admission.
- Potential eligible Subjects will be identified by screening the electronic health records (EHR). In addition, CHOP staff may notify the research personnel when there is a potential Subject.
- For a potential Subject who meets the inclusion/exclusion criteria, the Investigator will discuss the Study with the parent/guardian and obtain informed consent.
- Where appropriate, the Investigator will discuss the Study with the pediatric patient and obtain assent.

### 4.2 Study Treatment Phase

#### **General overview of Study Treatment Phase - Phase I:**

- Female patients  $\geq$  10 years of age or those who have experienced the onset of menses must have a documented NEGATIVE pregnancy test (urine or blood).
- Subject's most recent radiograph will be obtained and reviewed by the Investigator to identify EAD(P) characteristics and tube tip location, as well as pre-existing abnormalities, including damage to EAD(P) and/or tissue, if any.
- The Investigator has the option to order a new radiograph prior to the intervention if there is uncertainty about the status of the EAD(P) tube tip location and characteristics.
- The Subject's Nurse will obtain standard baseline measures of Subject pain.
- EAD(P) length will be determined by review of Subject EHR and/or markings on the EAD(P). The Investigator will place the Operator-set Collar to the same length determined by review of Subject's chart and/or markings on the EAD(P).
- Data will be gathered or abstracted from the EHR prior to, during the Subject receiving the intervention, and through the follow-up period. This data includes subject name, date of birth, contact information for parent/guardian, age, sex, race, ethnicity, weight, stature, BMI, location (PICU/PCU/IR), dates of hospitalization (length of stay), medical record number (MRN), contact serial number (CSN), diagnosis, procedures performed, medications administered, laboratory and radiology results, ventilator parameters (if ventilated), severity of illness, nutrition information, information on EAD and clog, and physical assessments with vital signs (patient temperature, heart rate, respiratory rate, blood pressure and pain level).

- The patient's Nurse will obtain standard measures of Subject pain following intervention.
- Intervention is deemed successful if EAD(P) is able to be flushed with 10 ml of air within five (5) minutes following the Intervention. The Intervention is deemed unsuccessful if EAD(P) is unable to be flushed with 10 ml of air within five (5) minutes following the Intervention.
- Subject will receive a portable abdominal radiograph with contrast agent following the intervention. The radiologist (blinded to the study) will assess and report the abdominal radiographs post-intervention for adverse events (i.e., EAD(P) displacement, EAD(P) damage, enteral tract tissue injury) attributable to the intervention. Study procedures carried out in IR may utilize low-dose fluoroscopy as an alternative to the portable abdominal radiograph.
- If the intervention is unable to restore EAD(P) patency, further steps to restore patency will be determined by the clinical team per usual practice.

### **General overview of Study Treatment Phase – Phase IIA**

- Female patients  $\geq$  10 years of age or those who have experienced the onset of menses must have a documented NEGATIVE pregnancy test (urine or blood).
- Subject's most recent radiograph will be obtained and reviewed by the Investigator to identify EAD(P) characteristics and tube tip location, as well as pre-existing abnormalities, including damage to EAD(P) and/or tissue, if any.
- The Investigator has the option to order a new radiograph prior to the intervention if there is uncertainty about the status of the EAD(P) tube tip location and characteristics.
- The Subject's Nurse will obtain standard baseline measures of Subject pain.
- EAD(P) length will be determined by review of Subject EHR and/or markings on the EAD(P). The Investigator will place the Operator-set Collar to the same length determined by review of Subject's chart and/or markings on the EAD(P).
- Data will be gathered or abstracted from the EHR prior to, during the Subject receiving the intervention, and through the follow-up period. This data includes subject name, date of birth, contact information for parent/guardian, age, sex, race, ethnicity, weight, stature, BMI, location (PICU/PCU/IR), dates of hospitalization (length of stay), medical record number (MRN), contact serial number (CSN), diagnosis, procedures performed, medications administered, laboratory and radiology results, ventilator parameters (if ventilated), severity of illness, nutrition information, information on EAD and clog, and physical assessments with vital signs (patient temperature, heart rate, respiratory rate, blood pressure and pain level).
- The patient's Nurse will obtain standard measures of Subject pain following intervention.

- Intervention is deemed successful if EAD(P) is able to be flushed with 10 ml of air within five (5) minutes following the Intervention. The Intervention is deemed unsuccessful if EAD(P) is unable to be flushed with 10 ml of air within five (5) minutes following the Intervention.
- Subject will receive a portable abdominal radiograph with contrast agent following the intervention. The radiologist (blinded to the study) will assess and report the abdominal radiographs post-intervention for adverse events (i.e., EAD(P) displacement, EAD(P) damage, enteral tract tissue injury) attributable to the intervention. Study procedures carried out in IR may utilize low-dose fluoroscopy as an alternative to the portable abdominal radiograph.
- If the intervention is unable to restore EAD(P) patency, further steps to restore patency will be determined by the clinical team per usual practice.

### **General overview of Study Treatment Phase – Phase IIB**

- Female patients  $\geq$  10 years of age or those who have experienced the onset of menses must have a documented NEGATIVE pregnancy test (urine or blood).
- Subject will be randomized to either TubeClear® intervention (experimental) or CHOP Standard Treatment (control) group according to randomization sequence.
- Subject's most recent radiograph will be obtained and reviewed by the Investigator to identify EAD(P) characteristics and tube tip location, as well as pre-existing abnormalities, including damage to EAD(P) and/or tissue, if any.
- The Investigator has the option to order a new radiograph prior to the intervention if there is uncertainty about the status of the EAD(P) tube tip location and characteristics.
- The Subject's Nurse will obtain standard baseline measures of Subject pain.
- Subject will receive TubeClear® intervention or CHOP Standard Treatment based on the randomization assignment.
- If randomized to TubeClear®, EAD(P) length will be determined by review of Subject's EHR and/or markings on the EAD(P). The Investigator will place the Operator-set Collar to the same length determined by review of Subject's chart and/or markings on the EAD(P). The TubeClear® Instructions for Use (i.e., Operator's Manual) will be followed by the user to restore patency to the EAD(P).
- If randomized to CHOP Standard Treatment, the CHOP protocol to restore patency to occluded EAD(P) will be followed.
- Data will be gathered or abstracted from the EHR prior to, during the Subject receiving either intervention, and through the follow-up period. This data includes subject name, date of birth, contact information for parent/guardian, age, sex, ethnicity, weight, stature, BMI, location (PICU/PCU/IR), dates of hospitalization (length of stay),

medical record number (MRN), contact serial number (CSN), diagnosis, procedures performed, medications administered, laboratory and radiology results, ventilator parameters (if ventilated), severity of illness, nutrition information, information on EAD and clog, and physical assessments with vital signs (patient temperature, heart rate, respiratory rate, blood pressure and pain level).

- Nursing assessment using the appropriate scale of the Subject's pain prior to and following the respective intervention will be abstracted from the medical record.
- Intervention in either group is deemed successful if EAD(P) is able to be flushed with 10 ml of air within five (5) minutes following the respective intervention. The intervention is deemed unsuccessful if EAD(P) is unable to be flushed with 10 ml of air within five (5) minutes following the intervention.
- Subject will receive a portable abdominal radiograph with contrast agent following either intervention. The radiologist (blinded to the study) will assess and report the abdominal radiographs post-intervention for adverse events (i.e., EAD(P) displacement, EAD(P) damage, enteral tract tissue injury) attributable to the intervention. Study procedures carried out in IR may utilize low-dose fluoroscopy as an alternative to the portable abdominal radiograph.
- In either group, if the intervention is unable to restore EAD(P) patency, further steps to restore patency will be determined by the clinical team per usual practice.

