**Figure 1: Study Flow Chart**

**Table 1. Schedule of Study Procedures**

Study Phase	PHASE I n=15	PHASE IIA	PHASE IIB
		n=15	n=34
Screening - Review Health Record for Eligibility	X	X	X
Informed Consent/Accent	X	X	X
Medical History/Labs/Medication/Health Record Review	X	X	X
Pregnancy Test, if not documented as completed in EMR	X	X	X
Radiograph Review – pre TubeClear® Intervention or Standard Treatment	X	X	X
Physical Exam/Pain Assessment Pre – Day of TubeClear® or Standard Treatment	X	X	X
Study Intervention - TubeClear® Intervention	X	X	
Randomization to TubeClear® Intervention or Standard Treatment			X
Physical Exam/Pain Assessment Post – Day of TubeClear® or Standard Treatment	X	X	X
Radiograph Review – Post TubeClear® Intervention or Standard Treatment	X	X	X
Physical Exam/Pain Assessment/ Day 1 Follow up	X	X	X
Physical Exam/Pain Assessment/ Day 2 Follow up	X	X	X
Physical Exam/Pain Assessment/ Day 3 Follow up	X	X	X
Adverse Event Assessment	X	X	X

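### Phase IIB vital-sign changes are compared without adjusting for the pre-intervention value already collected in both arms; as a minor point, the sections should agree that the envelope is opened after baseline recording

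*Combined protocol and SAP*

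**What the plan says.** **Vital signs.** Section 5.1.3 collects vital signs before, during and after the study interventions, with baseline and daily follow-up values taken from the health record. Section 6.3.4 item 3 compares the changes between the two Phase IIB arms by a t-test, or by an unnamed non-parametric equivalent if the distributions are not normal. No baseline covariate is specified. Section 6.3.2 mentions covariates only as an exploratory assessment and does not name the pre-intervention vital signs.

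**Order of events.** The Phase IIB overview in section 4.2 states, as its second bullet, "Subject will be randomized to either TubeClear® intervention (experimental) or CHOP Standard Treatment (control) group according to randomization sequence". Later bullets say "Subject's most recent radiograph will be obtained and reviewed by the Investigator", then "The Investigator has the option to order a new radiograph prior to the intervention if there is uncertainty", then "The Subject's Nurse will obtain standard baseline measures of Subject pain". Section 3.1.2 likewise begins by saying that "subjects will be randomized into either TubeClear® intervention or CHOP Standard Treatment using a predetermined computer generated randomization sequence stored in opaque sealed envelopes" and only then adds "Prior to the intervention, the location of the EAD(P) will be determined based on review of radiographs". Table 1 runs the other way: its row "Randomization to TubeClear® Intervention or Standard Treatment" stands below the pre-intervention radiograph row and the pre-intervention examination and pain row. Table 1 has no row for vital signs. The only rules on opening the envelope are in sections 3.2 and 9.1.1, and both require consent and enrolment and nothing else. Section 9.1.2 blinds the radiologist who reads the post-intervention films, but not the investigators, the study nurse or other research staff.

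**The concern.** A change score subtracts the whole of the pre-intervention value, which amounts to fixing its regression slope at 1. With equal variances the best slope is r, so unless r is close to 1 the change score carries avoidable noise. It also over-corrects any chance difference between the arms at baseline. With 17 per arm both effects can be noticeable, and the data needed to remove them are already collected.

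The order of events matters for a different reason. A reference value recorded before the envelope is opened cannot be influenced by the allocation. One recorded afterwards by unblinded staff could be. The rules on the envelope leave this open, and the sections do not list the steps in the same order.

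**Working it through.** **The plan's own figure.** Section 6.4 takes 95% against 50% success, alpha 0.05 and power of at least 0.80, and arrives at 17 per group. Taking alpha as two-sided (the plan does not say), exact enumeration for Fisher's test gives power 0.777 at 16 per group and 0.813 at 17. The 17 reproduces, and nothing below changes it.

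**Inputs for vital signs.** 17 per arm, alpha 0.05 (taken as two-sided) and 80% power come from section 6.4. The documents give neither a standard deviation nor a pre-post correlation. Assumptions: equal pre and post variances (SD = 1), 34 independent observations, and r from 0.3 to 0.9.

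**Formulas.**
- Change score: variance 2(1 − r), 32 degrees of freedom. The non-central t distribution gives a detectable standardised difference of 0.991, so the detectable difference is 0.991 × √(2(1 − r)).
- Covariate-adjusted: residual variance 1 − r², 31 degrees of freedom, standardised difference 0.992. Estimating the slope inflates the variance on average by 1 + 1/30 = 31/30. The detectable difference is 0.992 × √(1 − r²) × √(31/30).
- Variance ratio, adjusted to change: (1 − r²) / (2(1 − r)) = (1 + r)/2, and (1 + r)/2 × 31/30 after the cost of estimating the slope.

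Example at r = 0.5: change 0.991 × √1 = 0.991; adjusted 0.992 × √0.75 × √(31/30) = 0.873; variance ratio 0.75 × 31/30 = 0.775.

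| r | Net variance ratio | Variance reduction | Detectable, change (SD) | Detectable, adjusted (SD) | Change-score power at the adjusted difference |
|---|---|---|---|---|---|
| 0.3 | 0.672 | 33% | 1.17 | 0.96 | 0.63 |
| 0.5 | 0.775 | 23% | 0.99 | 0.87 | 0.69 |
| 0.7 | 0.878 | 12% | 0.77 | 0.72 | 0.75 |
| 0.8 | 0.930 | 7% | 0.63 | 0.61 | 0.77 |
| 0.9 | 0.982 | 2% | 0.443 | 0.440 | 0.79 |

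**Chance imbalance.** The standard error of a baseline difference is √(2/17) = 0.343 SD, so an absolute imbalance above 0.5 SD has probability of about 0.14. An imbalance of 0.5 SD shifts the change-score contrast by (1 − r) × 0.5 SD: 0.35, 0.25, 0.15, 0.10 and 0.05 SD at the five values of r.

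**Order of events.** No arithmetic applies. Side by side:
- Section 4.2 names randomisation before film review, the optional new film and baseline pain.
- Section 3.1.2 names randomisation before film review.
- Table 1 lists film review and pain above randomisation.
- Sections 3.2 and 9.1.1 set only consent and enrolment as conditions for opening the envelope.
- Sections 3.1.2 and 5.1.3 place the film review and the vital signs before the intervention, which is not the same as before allocation.

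None of these lists is declared chronological, so what can be established is a difference in listed order together with a rule that does not settle it.

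**The case against.** **The change score is already adequate.** It uses the pre-intervention value and is unbiased under randomisation. Vital signs are one of five secondary comparisons, and the plan powers nothing on them. All of this stands, and a reader who inferred that item 3 is an invalid test would be wrong. What remains is precision: small if r is 0.8 or more, useful if r is 0.5 or less.

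**A rank-based version of the adjusted model.** It is tempting to replace the non-parametric fallback as well, by fitting the same model to ranks. Simulation under normality does not support that as a general gain. At the adjusted differences above, the rank model has power of about 0.75 against 0.72 for the Wilcoxon test on changes at r = 0.7. The two are about level at r = 0.8, and the rank model is lower at r = 0.9 (about 0.70 against 0.76 to 0.77). The planned fallback should stay.

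**Repeated enrolment.** Section 3.1.1 lets a subject enrol up to three times. The figures above ignore repeats, as does the planned t-test, so they describe the case without them.

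**Table 1 already has the right order.** It is titled as the schedule, and section 4 refers to it for all phases. That is a fair reading for film review and pain, and it reduces this part to bringing sections 3.1.2 and 4.2 into line. It does not cover vital signs, and it is not a rule on opening the envelope.

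**Little is exposed.** No planned comparison in section 6.3.4 uses the investigator's pre-intervention film reading. Post-intervention films are read by the blinded radiologist. Baseline vital signs come from the health record. Section 4.2 also says of the nursing assessment that "pain prior to and following the respective intervention will be abstracted from the medical record", so it is not scored by the research team. That leaves nurse-rated baseline pain as the main plausible exposure, and post-intervention pain stays unblinded in any order.

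**Conclusion.** The main point is a free improvement to a secondary analysis. Adjusting for the pre-intervention value lowers the variance of the vital-sign comparison by between 33% (r = 0.3) and 2% (r = 0.9) net of its cost, and limits the effect of chance baseline imbalance. The range rests on assumed equal variances, independent observations and correlations that the documents do not give.

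The order of events is a minor matter of reconciliation. A reader might infer from section 4.2 that baseline measures are taken after allocation by design, or that the secondary results are biased. The documents do not support either: bullet order in a general overview is not a sequence, Table 1 points the other way, and no figure allows a bias to be sized. The air-flush primary endpoint and the 17 per arm are unaffected by both points.

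**What to change.** 1. Replace section 6.3.4 item 3 with: *Vital signs during and after the intervention are each compared between arms by a linear model with arm and the pre-intervention value as covariate; if the distributions are not normal, the planned non-parametric comparison of changes is kept.* This costs one degree of freedom and needs no new data, since a change score requires the same two readings.

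2. In sections 3.2 and 9.1.1 state that the envelope is opened after the pre-intervention film review, baseline pain and baseline vital signs have been recorded. Move the randomisation bullet in the Phase IIB part of section 4.2 below baseline pain, and the randomisation sentence in section 3.1.2 below the film review, to match Table 1. This costs one sentence and some reordering; the allocation becomes known slightly later.
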